## 13. Changes to the Planned Analysis

Not applicable.

## 14. Timing of the Analysis

No interim analysis is required. The final analysis will be performed after database lock and unblinding.

## 15. Software

SAS® Version 9.4 or higher (SAS Institute, Cary, North Carolina, USA) will be used for all non-pharmacokinetic analyses. NCA parameters will be calculated using PKNCA version 0.11 or higher.

## 17. Appendices

### APPENDIX A. REFERENCE RANGES FOR CLINICAL LAB TESTS

Category	Test	Reference Range
CBC, Platelets and Differential	White Blood Cell Count	4.16-9.95 x10E3/uL
	Red Blood Cell Count	3.96-5.09 (female); 4.41-5.95 (male)
	Hemoglobin	11.6-15.2 g/dL (female); 13.5-17.1 g/dL (male)
	Hematocrit	34.9-45.2% (female); 38.5-52.0% (male)
	Mean Corpuscular Volume	79.3-98.6 ng/mL
	Mean Corpuscular Hemoglobin	26.4-33.4 pg
	MCH Concentration	31.5-35.5 g/dL
Comprehensive Metabolic Panel	Albumin	3.9-5.0 g/dL
	Alkaline phosphatase	37-113 U/L
	Alanine Aminotransferase (ALT)*	8-70 U/L
	Aspartate Aminotransferase (AST)*	13-62 U/L
	Bilirubin, total*	0.1-1.2 mg/dL
	Calcium	8.6-10.4 mg/dL
	Chloride	96-106 mmol/L
	Total CO 2	20-30 mmol/L
	Creatinine	0.60-1.30 mg/dL
	Glucose	65-99 mg/dL
	Potassium	3.6-5.3 mmol/L
	Total Protein	6.1-8.2 g/dL
	Sodium	135-146 mmol/L
	Urea Nitrogen	7-22 mg/dL
Urinalysis	Specific Gravity	1.005-1.030
	pH	5.0-8.0
	Protein, Bilirubin, Glucose; Ketone bodies; Blood; Nitrates; Leukocyte	All Negative
	RBCs per $\mu$ L	0-11 cells/uL
	WBCs per $\mu$ L	0-22 cells/uL
	Squamous epithelial cells	0-17 cells/uL
Coagulation	INR*	In absence of anticoagulant therapy: < 1.1 Therapeutic range: 2-3; Mechanical valves: 2.5-3.5
Additional Tests, Hormone	Estradiol	Female: Prepubertal: <12 pg/mL; Postmenopausal: <21 pg/mL; Follicular phase: 20-100 pg/mL; Mid-cycle: 80-400 pg/mL; Luteal phase: 30-220 pg/mL Male: Prepubertal <12 pg/mL; Adult <41 pg/mL
	Prolactin	Female: 3-23.1 ng/mL; Male: 3.8-18.9 ng/mL
	FSH Blood	Female: Prepubertal: 1-6 mIU/mL; Pregnant: <6 mIU/mL; Postmenopausal: 21-106 mIU/mL; Follicular phase: 2-8 mIU/mL; Mid-cycle: 6-23 mIU/mL; Luteal phase: 1-6 mIU/mL Male: Prepubertal: 1-6 mIU/mL; Adult 1.6-9 mIU/mL
	LH	Female: Prepubertal: 1-3 mIU/mL; Postmenopausal: 16-63 mIU/mL; Follicular phase: 2-15 mIU/mL; Mid-cycle: 10-91 mIU/mL; Luteal phase: 1-15 mIU/mL Male: Prepubertal: 1-3 mIU/mL; Adult: 2-12 mIU/mL
	TSH	0.3-4.7 mIU/mL
	T 4 , Total	4.90-11.40 mcg/dL
	T 3 , Total	85-185 ng/dL
	Free T 4	4.5-10.5 ng/dL

\*Key lab endpoints

## APPENDIX B. CRITERIA FOR POTENTIALLY CLINICALLY SIGNIFICANT ABNORMALITIES (PCSA)

Potentially clinically significant abnormality (PCSA) values are defined as abnormal values considered medically important by the Sponsor (NIDA) according to predefined criteria/thresholds based on literature review and defined by the Sponsor. Given the literature and safety findings with Epidiolex®, a currently FDA-approved and marketed drug, and considering the possibility of untoward drug-drug interactions of CBD with buprenorphine, PCSA criteria are related to potential drug-induced liver injury, blood clotting, hypoxia related to an effect of CBD on buprenorphine metabolism, and ovarian suppression.

### Potential Cases of Drug-Induced Liver Injury

The threshold of laboratory abnormalities for a potential case of drug-induced liver injury depends on the subject's individual baseline values and underlying conditions. Subjects who present with the following laboratory abnormalities should be considered as meeting criteria for a PCSA:

1. Subjects with AST or ALT and total bilirubin baseline values within the normal range who subsequently present with AST or ALT  $\geq$  3 times the upper limit of normal (X ULN) concurrent with total bilirubin  $\geq$  2 X ULN with no evidence of hemolysis and alkaline phosphatase  $\leq$  2 X ULN or not available.
2. For subjects with preexisting ALT **OR**, AST **OR** total bilirubin values above the upper limit of normal, the following threshold values should be used in the definition mentioned above:  
AST or ALT  $\geq$  2 times the baseline values and  $\geq$  3 X ULN, or  $\geq$  8 X ULN (whichever is smaller).
3. For subjects with pre-existing values of total bilirubin above the normal range: total bilirubin increased by one time the upper limit of normal or  $\geq$  3 times the upper limit of normal (whichever is smaller).

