Exclusion criteria also include clinically significant medical conditions; and AIDS or current HIV seropositivity (as HIV positive individuals entering the Tarzana Treatment Center generally have medication treatment with antiviral and/or non-antiviral therapies that have potential interactions with CBD). Pregnancy and lactation also will be exclusion criteria. Because of evidence that CBD affects ovarian function, women with hormone values outside the normal range on a test battery will be evaluated with ultrasound; those who have evidence of ovarian suppression will be excluded.

Screening labs/tests will include direct bilirubin (D Bili) and liver function tests (LFT), baseline ECG, and pregnancy test for women. Parameters for exclusion include:

- a. AST or ALT greater than or equal to 3Xs ULN.
- b. Bilirubin greater than or equal to 1.5 Xs ULN.
- c. Clinically significant abnormalities on EKG

d. Pregnancy test positive.

Based on Epidiolex® (CBD oral solution) label section 7, "Drug Interactions", we will exclude participants who are taking the following medications: strong a) inducers of CYP3A4 or CYP2C19 (e.g., rifampin, due to the potential to decrease CBD plasma levels); and b) substrates of UGT1A9 (e.g., diflunisal, propofol, fenofibrate), UGT2B7 (e.g., gemfibrozil, lamotrigine, morphine, lorazepam), CYP2B6 (e.g., bupropion, efavirenz), CYP2C19 (e.g., clobazam, diazepam) due to potential to inhibition of enzyme activity by CBD).

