- **Repeat/unscheduled assessments:** Only values collected at scheduled study visits/time points will be presented in summary tables. Unscheduled visit data may be included in summaries of baseline, minimum/maximum post-baseline, and incidence of subjects with potentially

clinically significant post-baseline results. Unscheduled visits will also be presented in the applicable data listings.

- Assessment windows: Data will be summarized using the recorded nominal visit values in the CRF; no visit date windowing will be conducted. All assessments will be included in the data listings.
- Date and time display conventions: The following display conventions will be applied in all outputs where dates and/or times are displayed:

Date only: YYYY-MM-DD

Date and time: YYYY-MM-DD HH:MM

If only partial information is available, unknown components of the date or time will be presented as 'NK' (not known), i.e., '2016-NK-NK'. Times will be reported in military time.

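### The liver PCSA rule counts a transaminase rise only when bilirubin rises with it, and no planned table counts participants by multiple of ULN

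*SAP*

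**What the plan says.** SAP Appendix B, under potential cases of drug-induced liver injury, has three items.

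- Item 1 covers participants with normal baseline values. It needs AST or ALT of at least "3 times the upper limit of normal (X ULN) concurrent with total bilirubin" of at least 2 × ULN, "with no evidence of hemolysis and alkaline phosphatase" no higher than 2 × ULN or not available.
- Item 2 covers participants whose ALT, AST or bilirubin was already raised. It states that "the following threshold values should be used in the definition mentioned above", then gives AST or ALT of at least 2 × baseline and at least 3 × ULN, or at least 8 × ULN, whichever is smaller.
- Item 3 covers raised baseline bilirubin. It gives "total bilirubin increased by one time the upper limit of normal or" at least 3 × ULN, whichever is smaller.

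None of the other PCSA criteria in Appendix B uses ALT or AST.

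Elsewhere in the SAP:

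- Section 3.4 makes change in liver enzymes a secondary endpoint under the primary safety objective.
- Appendix A stars ALT, AST, total bilirubin and INR as key laboratory endpoints.
- Section 10.2 tabulates and lists the key laboratory parameters and does not mention Appendix B.
- Section 4.1 sets the default continuous summary (n, mean, SD, median, minimum, maximum) and rules out inferential statistics for safety.
- Section 4.1 also says "Unscheduled visit data may be included in summaries of baseline, minimum/maximum post-baseline, and incidence of subjects with potentially" clinically significant results after baseline.

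The protocol's screening laboratory exclusions include "AST or ALT greater than or equal to 3Xs ULN" and, as a separate item, "Bilirubin greater than or equal to 1.5 Xs ULN".

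**The concern.** Appendix B names liver injury first among its PCSA concerns and refers to safety findings with a marketed CBD product. Yet the only rule that turns a transaminase value into a countable event also requires a bilirubin value, so the count is limited to the severe end of the liver signal.

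A participant whose ALT rises sharply while bilirubin stays below its limit adds nothing to that count. The other planned laboratory output is a mean/SD/median/minimum/maximum summary by arm and visit. It can show that one participant had a high value, but not how many participants in each arm passed a given level.

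Safety is the primary objective and is purely descriptive, so counts per arm are much of the evidence a reader will have. A peak seen only at an unscheduled visit might enter no table at all, because including it is optional.

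**Working it through.** The plan states no figure for this rule, so there is nothing to reproduce. The check applies the rule to values and then compares the planned outputs.

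**1. Cut-offs from Appendix A.** The ULNs are ALT 70 U/L, AST 62 U/L, total bilirubin 1.2 mg/dL and alkaline phosphatase 113 U/L.

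- 3 × ULN: ALT 3 × 70 = 210; AST 3 × 62 = 186.
- 2 × ULN: bilirubin 2 × 1.2 = 2.4; alkaline phosphatase 2 × 113 = 226.

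**2. Normal baseline (item 1), with the hemolysis and alkaline phosphatase conditions met.**

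| ALT | Bilirubin | PCSA? |
|---|---|---|
| 210 U/L (3 × ULN) | 2.4 mg/dL (2 × ULN) | yes |
| 700 U/L (10 × ULN) | 2.3 mg/dL (2.3/1.2 = 1.92 × ULN) | no |
| 1400 U/L (20 × ULN) | 1.99 × ULN | no |

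**3. Raised baseline, with items 2 and 3 read as replacement thresholds inside item 1.** In multiples of ULN, the transaminase threshold is min(max(2 × baseline, 3), 8). The threshold for a raised baseline bilirubin is min(baseline + 1, 3).

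- Transaminase baselines of 0.8, 1.5, 2.0 and 2.9 give thresholds of 3, 3, 4 and 5.8.
- Bilirubin baselines of 0.8, 1.2 and 1.5 give thresholds of 2, 2.2 and 2.5.
- Isolated transaminase rises of 3, 5, 8, 10, 20 and 50 × ULN, with bilirubin held at baseline, are flagged in none of the 12 combinations.
- The 8 × ULN alternative never applies to an eligible participant: a baseline below 3 × ULN puts twice the baseline below 6 × ULN.

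**4. Item 2 read as stand-alone instead.** Isolated rises would then be flagged in raised-baseline participants, from 3 to 5.8 × ULN upward depending on baseline. They would still never be flagged in normal-baseline participants, so the result for that group does not depend on the reading.

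**5. Where an isolated rise would appear.**

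| Output | Shows the value? | Counts participants per arm above a ULN multiple? |
|---|---|---|
| Key laboratory summary (10.2, 4.1) | yes, as a visit maximum if scheduled | no |
| Laboratory listing (10.2) | yes | no |
| TEAE tables (10.1) | only if recorded as an event | no |
| Liver PCSA (Appendix B) | no | joint criterion only |

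**6. Illustration of size.** Let n be the number of exposed CBD participants, p the proportion reaching ALT/AST ≥3 × ULN, and c the proportion of those who also meet the bilirubin limit. With independent participants, P(any case) is 1 − (1 − p)^n for transaminases alone and 1 − (1 − pc)^n for the joint rule.

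Section 3.1 expects 21 participants in the CBD arm and reports 6 randomized participants who were never dosed, without giving their arm. So n lies between 21 − 6 = 15 and 21. If the undosed split 2:1 and all seven later participants were dosed, n = (28 − 6) × 2/3 + 7 × 1/3 = 17. The documents give neither p nor c; both are assumed.

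| n | p | c | Joint rule | Transaminases alone |
|---|---|---|---|---|
| 15 | 10% | 1 in 10 | 1 − 0.99^15 = 14% | 1 − 0.90^15 = 79% |
| 17 | 10% | 1 in 10 | 1 − 0.99^17 = 16% | 1 − 0.90^17 = 83% |
| 21 | 10% | 1 in 10 | 1 − 0.99^21 = 19% | 1 − 0.90^21 = 89% |
| 17 | 5% | 1 in 10 | 1 − 0.995^17 = 8% | 1 − 0.95^17 = 58% |
| 17 | 2% | 1 in 10 | 1 − 0.998^17 = 3% | 1 − 0.98^17 = 29% |
| 17 | 10% | 3 in 10 | 1 − 0.97^17 = 40% | 83% |

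The size of the gap follows the assumed coupling. Its direction does not: every threshold in items 1 and 2 is at least 3 × ULN, so the joint count can never exceed the transaminase count.

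**The case against.** The strongest reply is that nothing is hidden. ALT and AST are key laboratory endpoints, so a scheduled value of 700 U/L would appear as that arm's maximum and in the listing, and it could be recorded as an adverse event. With about 35 participants, a reader can find every case in the listing. The rule is also headed as potential drug-induced liver injury, which is narrower than all notable liver results, and the sponsor set its thresholds after a literature review. All of this stands, and it limits the point to missing counts under a label. It does not remove it, because neither a maximum nor a listing is a tabulated count per arm.

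Three stronger readings are tempting, and the documents do not support them.

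- A reader might infer that the plan contradicts itself because ALT or AST at 3 × ULN alone bars entry. An entry limit screens out existing abnormality, whereas the PCSA rule classifies changes on treatment. The two may differ.
- A reader might infer that item 3 flags bilirubin alone in participants with a raised baseline, while no such flag exists for a normal baseline. That takes item 3 as stand-alone and item 2 as a substitution. Read in the same way, both only replace thresholds in the joint definition, and the asymmetry disappears. The wording is loose enough to need clarifying.
- A reader might infer that the PCSA count is bound to be zero in both arms. The documents give no event rates. Even the 10%, 1-in-10 illustration leaves a 14–19% chance of a CBD case, and 3-in-10 coupling raises it to 40%.

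The reply is also right that Section 10.2 never cites Appendix B, and that PCSA incidence is mentioned only in the bullet on unscheduled visits. That is a further gap in the SAP, and the fix should close it.

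**Conclusion.** The point holds in a limited form. For participants with normal baseline values, the liver PCSA does not count an isolated transaminase rise of any height. The same is true of raised-baseline participants if item 2 is taken as the substitution it says it is. Such rises remain visible in summaries and listings, but no planned output counts participants per arm by multiple of ULN for a named secondary safety endpoint.

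The conclusion about the rule needs only the SAP text and the Appendix A limits. The probabilities (about 14–19% against 79–89% for 15 to 21 CBD participants) rest on an assumed 10% rate, an assumed 1-in-10 coupling and independence. They illustrate the gap and are not a forecast. This is a cheap improvement to safety reporting. No planned inference is affected, since the SAP plans none for safety.

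**What to change.** Before database lock:

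- **Appendix B, table rows.** Keep the joint criterion as its own row. Add counts of participants per arm for worst post-baseline ALT or AST ≥3 × ULN and ≥8 × ULN regardless of bilirubin, and for total bilirubin ≥2 × ULN regardless of transaminases. These multiples already appear in Appendix B, though only inside the joint rule.
- **Appendix B, items 2 and 3.** State that both are replacement thresholds within the joint definition.
- **Section 10.2.** Refer to this table, so that the PCSA criteria lead to a named output.
- **Section 4.1.** State that unscheduled results will be included in worst-value and PCSA incidence summaries.

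The cost is some SAP wording and three table rows on data already collected. Eligibility, dosing and stopping are untouched. The downside is that some flagged values will have no clinical consequence. Keeping the joint row separate lets readers tell the two apart.

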### Potential Cases of Drug-Drug Interaction to induced Increase in Blood Clotting

Increase in buprenorphine levels with excessive sedation and slow respiratory rate, with hypoxia (<90%) on room air. Sedation is assessed with the Observed Observer's Assessment of Alertness/Sedation Scale (OAAS) with pulse oximetry data. A score of <4 on the OAAS scale or pulse oxygen saturation less than 92% in room air.

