**Study Periods:** The study design comprised four phases: 1) a 14-day screening period during which patients were consented, evaluated against entry criteria, and stabilized on buprenorphine; 2) randomization and baseline evaluation (Day 0); 3) a 28-day acute treatment period when each participant received the IMP twice daily (CBD or placebo); primary data collection phase, and 4) a 28-day follow-up period after termination of treatment with study medication (secondary data collection phase). Safety assessments included clinical lab tests during screening and weekly during the treatment and follow-up periods. On each study day, vital signs were taken, and patients reported adverse events, which were monitored and recorded. Although not a direct measure of safety, change in buprenorphine metabolism, operationalized as the ratio of buprenorphine to norbuprenorphine in plasma, was obtained, as out of range values occurring in the context of hypoxia and/or sedation could be indicative of increased risk. Because CBD inhibits CYP3A, the primary mechanism for hepatic buprenorphine N-dealkylation, the buprenorphine to norbuprenorphine ratio was measured in blood drawn for relevant PK analyses at baseline and weekly during the treatment and follow-up periods. Cue-induced craving was measured in laboratory sessions with a paradigm in which neutral and opioid-related cues were presented. These sessions were conducted before dosing on Day 0 (Baseline) and on Days 7 and 28 after study drug initiation (Treatment Phase).

The original protocol was approved by the FDA on October 12, 2020 (IND 152888). Modifications were needed because the approved investigational product became unavailable. On October 27, 2021, the FDA approved using ATL5 (100 mg/ml CBD softgel capsules) and matching placebo as the investigational medicinal products (IMPs), and testing two ascending-dose cohorts [cohort 1: CBD 600 mg/day, N = 20 and placebo (N = 10); cohort 2: CBD 1200 mg/day, N = 20 and placebo, N = 10)], each randomized 2:1 CBD:placebo, with the combined placebo subsamples intended to be treated as a common reference for both drug groups. The trial commenced in March 2022.

[figure not shown]
Randomization was stratified by baseline (i.e. post-stabilization period) plasma buprenorphine level—either < 2 ng/mL or ≥ 2 ng/mL—measured immediately prior to randomization and the daily dose of buprenorphine.

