### 3.4. Objectives and Endpoints

Objectives	Endpoints
Primary: To evaluate the safety and tolerability of CBD in the study population.	Primary: Number of treatment-emergent adverse events over the 28-day treatment period by study arm. Secondary: Changes in liver enzymes, pulse oximetry, sedation, and cardiovascular measures (heart rate, blood pressure, and cardiac rhythm and conduction on EKG).
Secondary: To determine the extent to which CBD (600 mg/day) reduces cue-induced craving for opioids relative to placebo.	Primary: Cue-induced craving for opioids, assessed using the Desires for Drug Questionnaire (DDQ)  in the context of an opioid cue-induction paradigm, assessed in the laboratory session before CBD dosing on Day 0 (baseline without CBD) and on Days 7 and 28 (after adjunctive treatment with CBD) Secondary: Spontaneous opioid craving, assessed using the Penn Alcohol-Craving Scale, as modified to assess opioid craving;  affect, assessed using the Positive and Negative Affect Schedule (PANAS),  Anxiety, assessed by state subscale of the Spielberger State-Trait Anxiety Inventory,  Percentage of patients with increase in their buprenorphine dose, Treatment retention, as indicated by number of days of continued participation
Exploratory: A. To evaluate effects of CBD on metabolism of other endocannabinoids, i.e., N-arachidonylethanolamide (anandamide) and 2-arachidonoyl-glycerol (2-AG) levels. B. To assess pharmacokinetics of CBD in patients receiving buprenorphine for treatment of OUD.	Plasma levels of anandamide and 2-AG. CBD pharmacokinetics—time to reach steady state and accumulation parameters (C max , AUC 0-24 ). In addition, the buprenorphine/norbuprenorphine ratio will be determined to evaluate potential drug-drug interactions of CBD with buprenorphine metabolism (dealkylation). Although this ratio does not, by itself, an increase in the ratio, concurrent with the emergence of hypoxia and/or sedation would be an AE.

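### SAP Appendix B gives two incompatible criteria for a hypoxia/sedation abnormality, and section 10 plans no summary of pulse oximetry or sedation

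*SAP*

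**What the plan says.** SAP Appendix B lists criteria for PCSAs. The hypoxia/sedation text stands under the heading "Potential Cases of Drug-Drug Interaction to induced Increase in Blood Clotting". It opens with "Increase in buprenorphine levels with excessive sedation and slow respiratory rate, with hypoxia (<90%) on room air", then says that sedation is assessed with the OAAS together with oximetry, and closes with "A score of <4 on the OAAS scale or pulse oxygen saturation less than 92% in room air". It contains no clotting criterion.

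SAP 3.4 sets the primary safety endpoint as "Number of treatment-emergent adverse events over the 28-day treatment period by study arm" and lists as secondary "Changes in liver enzymes, pulse oximetry, sedation, and cardiovascular measures". The exploratory row of the same table adds that "an increase in the ratio, concurrent with the emergence of hypoxia and/or sedation would be an AE". SAP 3.1 is softer: "out of range values occurring in the context of hypoxia and/or sedation could be indicative of increased risk". It places the ratio in "relevant PK analyses at baseline and weekly during the treatment and follow-up periods".

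SAP 10.1 to 10.4 cover adverse events, laboratory tests, vital signs and concomitant medication. The vital signs in 10.3 do not include oxygen saturation, and none of the four subsections mentions the OAAS.

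The protocol schedules oximetry and the OAAS on every treatment day (Safety Assessments and Monitoring, item b). Its Study Objectives predict that CBD will raise the buprenorphine/norbuprenorphine ratio.

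**The concern.** A PCSA rule should give the same answer whoever applies it. Here one sentence needs four findings at once and the other needs either of two. Their saturation cut-offs differ, and nothing says which sentence governs. SAP 4.1 refers to the incidence of participants with potentially clinically significant results, so the by-arm figure would depend on an unstated choice. If that choice is made after unblinding, it can look data-driven.

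The 3.4 clause raises a second issue. It makes a rise in the ratio a condition for calling hypoxia or sedation an adverse event. Treatment is expected to change the ratio, so equal rates of hypoxia or sedation need not give equal counts by arm.

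Third, without a planned summary of oximetry or the OAAS, two named safety endpoints have no specified output, and borderline saturations would appear only in listings, if at all.

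**Working it through.** The plan states no figure on this point, so there is none to reproduce; its power figure concerns craving.

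**The texts side by side**

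| Place | Buprenorphine condition | Saturation | Sedation | How joined |
|---|---|---|---|---|
| Appendix B, first sentence | raised level | <90% | excessive, no score | all together, plus slow breathing |
| Appendix B, closing sentence | none | <92% | OAAS <4 | either |
| SAP 3.4 | increase in ratio, no threshold | no cut-off | no cut-off | ratio plus either or both |
| SAP 3.1 | ratio out of range, no range given | no cut-off | no cut-off | possible sign of risk |
| Protocol, Interventions and Stopping Criteria, item b | none | <90% | score <4 | either |

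**Logic check.** The grid takes saturation 89, 90, 91, 92, 93 and 95%; OAAS 5, 4 and 3; and slow breathing yes or no: 6 × 3 × 2 = 36 profiles, with raised buprenorphine assumed throughout. Excessive sedation is taken as OAAS <4.

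- First sentence: only 89%, OAAS 3, slow breathing qualifies: 1 of 36.
- Closing sentence: OAAS <4 gives 12 profiles, saturation <92% gives 18, and 6 meet both: 12 + 18 − 6 = 24 of 36.
- Every profile meeting the first sentence also meets the closing one, so they disagree on 24 − 1 = 23.
- If the closing sentence only defines sedation within the first: 3 of 36. Any saturation below 90% is already below 92%, so the OAAS score then adds nothing.
- OAAS <4 or saturation <90%: 6 + 12 − 2 = 16 of 36. The 8 profiles lost against <92% all have saturation 90 or 91% with OAAS 4 or 5.

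Two examples. Saturation 91% with OAAS 5 is a PCSA under the closing sentence only. Saturation 95% with OAAS 3 sends the participant to the emergency department under protocol item b, yet is not a PCSA under the first sentence.

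**Size by arm.** SAP 3.1 gives 28 + 7 = 35 randomized, 6 known to be undosed, so at most 29 dosed. Scaled to the expected 21:14, this is 29 × 21/35 = 17.4 on CBD and 29 × 14/35 = 11.6 on placebo. One participant is then 1/17.4 = 5.7% or 1/11.6 = 8.6% of an arm. Let q be the share of participants who meet the closing sentence but never the first. The documents give no value, so q is assumed:

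| q | Extra PCSA participants, CBD | Extra, placebo |
|---|---|---|
| 0% | 0 | 0 |
| 5% | 0.87 | 0.58 |
| 10% | 1.74 | 1.16 |
| 20% | 3.48 | 2.32 |

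**The ratio condition in 3.4.** Suppose hypoxia/sedation rates are equal in both arms and unrelated to the ratio, any rise over Day 0 counts, and each episode is matched to one later draw. On placebo the draw exceeds Day 0 with probability 1/2. On CBD the probability lies between 1/2 and 1, so the CBD:placebo ratio of such events per participant lies between 1.0 and 2.0. For an assumed 1.5-fold CBD effect and within-person coefficient of variation CV, p = Φ(ln 1.5 / (√2·s)) with s = √ln(1 + CV²):

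- CV 20%: p = 0.93, ratio 1.85
- CV 30%: p = 0.84, ratio 1.67
- CV 50%: p = 0.73, ratio 1.46

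The clause also leaves the required timing of the ratio rise open. With weekly draws, a one-day episode at a random time coincides with a draw day with chance 4/28 = 14%. The schedule table is damaged, but its PK row suggests a further Day 3 draw, which would give 5/28 = 18%.

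**The case against.** A reader might infer that the primary endpoint is undefined, so that two analysts would report different adverse event counts. The documents do not support that. Appendix B defines PCSAs, and neither 3.4 nor 10.1 cites it. SAP 3.1 and 10.1 describe adverse events as reported and recorded; nothing tells an analyst to construct them from oximetry, OAAS and PK data. The 3.4 clause stands in the exploratory row, in a sentence that is incomplete as it reads. Saturation below 90% or a score below 4 already sends the participant to the emergency department, so it would very probably be recorded as an event whatever the ratio. Safety results carry no inference (SAP 4.1). This part of the objection stands and confines the effect on the event count to something small or zero.

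A reader might also count the protocol's <94% and <90% as a further conflict. They are graded actions: the first, over two consecutive days, stops dosing; the second triggers referral.

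It can be argued that tying hypoxia to buprenorphine is deliberate, since Appendix B is looking for a drug interaction. That is a good reason to show the ratio or level beside each case. It does not justify making it a condition for counting a safety event, and it does not reconcile the two sentences.

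**Conclusion.** The point holds for PCSA classification and for the missing summaries. Appendix B cannot be applied as written: its two sentences disagree on 23 of 36 illustrative profiles, and each reclassified participant would move an arm's percentage by about 6 points on CBD or 9 on placebo. That assumes 29 dosed, split in the expected proportion. How many participants would be reclassified is unknown and may be none.

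The 3.4 clause would tilt any event classified under it in favour of placebo, by a factor between 1.0 and 2.0 per participant under the stated assumptions. The factor applies only to events that depend on the clause, not to the whole count. No significance level or power figure changes. Section 10 omits both oximetry and sedation whichever criterion is preferred.

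**What to change.** Before database lock and unblinding:

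1. Retitle the Appendix B text as Hypoxia/sedation and use one PCSA rule: OAAS below 4 or saturation below 90% on room air at any Day 1-28 assessment, matching item b of the protocol's stopping criteria. List the ratio or buprenorphine level beside each case, but do not require it.
2. Amend the 3.4 clause: a hypoxia or sedation episode that is new or worse than at Screening is an adverse event whatever the ratio. Count it once and reconcile it with events that staff have already recorded, so that emergency referrals are not counted twice.
3. Add to section 10, by arm: participants meeting the PCSA rule; lowest Day 1-28 saturation, with counts below 92% and below 94%; and lowest OAAS.
4. Keep blood clotting in Appendix B as a separate item with its own INR criterion. The SAP names it as a PCSA topic and INR is a key laboratory test, so it should not be dropped. The sponsor must set the threshold, since the documents give only reference ranges.

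The cost is a few lines in 3.4, section 10 and Appendix B, plus a short table. Oximetry and OAAS are already scheduled daily, so no new data or protocol change is needed. The downside is that <90% is less sensitive than <92%; the lowest-saturation summary keeps those readings visible.
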